3.2.3 Dosing schedule

All doses of study drug will be taken at the investigative site. [REDACTED]

[REDACTED]

[REDACTED]

[REDACTED]

[REDACTED]

[REDACTED]

3.2.4 Participant compliance

The Investigator may withdraw a participant from the study or discontinue study drug for any of the following reasons:

- Noncompliance with protocol procedures, including those relating to administration of study drug
- Occurrence of a serious adverse event (SAE) or intolerable adverse event (AE)
- Occurrence of a clinically significant change in a laboratory parameter

[REDACTED]

[REDACTED]

[REDACTED]

[REDACTED]

[REDACTED]

- Termination of the study by the Sponsor or Investigator
- The participant requests to be discontinued from the study

Participants who discontinue study drug (regardless of reason) will be asked to remain in the study to complete all remaining assessments until hospital discharge or Day 28, whichever is sooner, unless they withdraw consent or are lost to follow-up. If this is not feasible, the participant will be assessed for an early termination visit. All assessments that are required at the last study visit, as shown in [Appendix A](#), should be completed for any participant who is withdrawn from the study or prematurely discontinues study drug and does not agree to complete all remaining assessments.

4. GENERAL CONSIDERATIONS FOR DATA ANALYSIS

With the availability of COVID-19 vaccines beginning in the fourth quarter of 2020, as well as the increased and successful measures taken to contain the virus, a dramatic decrease in the number of patients with ARDS associated with severe and critical COVID-19 was observed. Given the current and predicted decline in potential study participants, the study was terminated by the Sponsor. No statistical hypotheses will be tested. Unless otherwise specified, continuous data will be summarized using descriptive statistics (n, mean, standard deviation (SD), median, minimum, and maximum). Categorical variables will be summarized showing the number and percentage of participants within each category. All tabulations will be based on pooled data across centers.

Analyses will be performed using SAS for Windows statistical software, version 9.4 or higher (SAS, Cary, NC), except where other software may be deemed more appropriate.

████████ will perform all efficacy and safety analyses described in this SAP. ██████████ will perform pharmacokinetic analysis. Pharmacodynamic analysis will be performed by ██████████. ██████████.

Participant data will be listed, sorted by treatment arm, cohort, investigative center, and participant number. When applicable, listings will be additionally sorted by visit and assessment date/time.

4.1 Data Quality Assurance

Once all the source verification is complete, all queries are resolved, and the database has been updated appropriately, the database will be locked and made available to █████ Biostatistics for final analysis.

Data may be pulled by █████ Biostatistics for DSMB analysis at a time when source verification and query resolution is ongoing.

All SAS programs used to create analysis data sets, tables, and listings are double programmed.

The SAS outputs will be compared and the programs will be updated until the outputs match.

4.2 Analysis Sets

The following analysis sets will be defined for this study:

Safety Set: The Safety Set will consist of all randomized participants who receive at least 1 dose of study drug.

PK Concentration Set: all randomized participants who receive at least 1 dose of study drug and have any measurable PLN-74809 concentration data.

4.3 Assessment Windows

All data will be included in the analysis based on the visit recorded in the database.

4.4 Handling of Dropouts or Missing Data

Missing data on demographic, baseline information and safety will be treated as missing; no method for imputation is planned.

Details of any missing data imputation will be specified in the analysis methods for each of the exploratory efficacy endpoints.

4.5 Multiple Comparisons

No hypotheses are being tested.

4.6 Data Derivations and Transformations

The following derivations will be used in this study:

Study day:

- Date of assessment – date of study drug administration + 1 for assessments done on or after date of study drug administration
- Date of assessment – date of study drug administration for assessments done before date of study drug administration

Baseline value: the last non-missing value prior to study drug administration.

Shift from baseline: current value – baseline value. Although generally reserved for quantitative variables, it is also applied to some numeric ordinals

5. STUDY PARTICIPANTS

5.1 Disposition of Participants

A table of frequency counts and percentages of all participants in the Safety and PK Concentration sets will be provided. Participant disposition including study completion status and reasons for early termination (if applicable) will be tabulated by treatment arm and overall. A by participant listing will be provided.

5.2 Protocol Deviations

A listing of all protocol deviations will be provided.

5.3 Demographic Characteristics

Descriptive statistics will be used to summarize the demographic characteristics (age, sex, race, ethnicity, height, weight) for the participants in the Safety Set. A by participant listing will be provided.

5.4 Baseline Characteristics

Descriptive statistics will be used to summarize the baseline characteristics [REDACTED] for the participants in the Safety Set.

5.5 Medical History

All medical conditions and surgical procedures will be classified by system organ class (SOC) and preferred term (PT) using the Medical Dictionary for Regulatory Activities (MedDRA) version 23.0. The number and percent of participants with each medical condition and surgical procedure will be presented for each SOC and PT for the Safety Set. A listing will also be provided.

5.6 Concomitant Medications/Therapies

5.6.1 Medications

Concomitant medications/therapies collected will be coded using the March 2021 B3 WHO-Drug Dictionary. A listing of medications will also be provided.

5.6.2 Non- drug therapy

Non- drug therapies (e.g., ice pack, intubation, tracheostomy, ECMO) will be coded using MedDRA (version 23.0). A listing of non-drug therapy will be provided.

6. EFFICACY ANALYSES

The PK analyses will be performed using the PK Concentration set. All other exploratory efficacy summaries will be conducted using the Safety Set.

6.1 Pharmacokinetic Endpoints and Analysis

Blood samples for determination of plasma levels of PLN-74809 will be obtained at the following timepoints:

- Day 1: 0.5 hours (± 15 min), 3 hours (± 60 min), and 10 hours (± 120 min) postdose
- Day 7: predose, 3 hours (± 60 min), and 24 hours (± 60 min) postdose
- Day 14: predose for participants on study drug

If the participant is no longer being treated with study drug, discontinues the study early, or is not treated with study drug on Day 14, a single plasma sample for PK should be taken at the Day 14/end of treatment (EoT)/ early termination (ET) visit, if possible. Actual PK sample collection time and dosing time will be recorded. The PK sampling schema may be modified based on emerging data.

A listing of concentration values will be provided.

6.2 Exploratory Efficacy Endpoints and Analysis

6.2.1 Efficacy

The following will be summarized by treatment arm and applicable visit:

Term	Percentage
GMOs	85%
Organic	95%
Natural	90%
Artificial	75%
Organic	95%
Natural	90%
Artificial	75%
Organic	95%
Natural	90%
Artificial	75%
Organic	95%
Natural	90%
Artificial	75%

6.2.2 Pharmacodynamics

Plasma and serum and will be analyzed for biomarkers (presence or actual concentration). These samples will be used to determine the levels of biomarkers in participants and the relationship between these markers.

The PD analysis will be performed by [REDACTED]. Available biomarkers [REDACTED] will be summarized by visit and treatment arm. A listing of available biomarker concentration will be provided.

7. SAFETY ANALYSIS

Safety assessments will include assessment of AEs, laboratory parameters, vital signs, and [REDACTED]. All safety summaries (or analyses if applicable) will be conducted using the Safety Set. No formal hypothesis testing will be performed to compare differences between treatment arms.

7.1 Extent of Exposure

The number of tablets received, the occurrence of dose interruption, the duration of interruption, and total amounts of PLN-74809 in mg will be tabulated.

7.2 Adverse Events

An AE is any event, side effect, or other untoward medical occurrence that occurs in conjunction with the use of a study drug in humans, whether or not considered to have a causal relationship to this treatment. An AE can, therefore, be any unfavorable and unintended sign (that could include a clinically significant abnormal laboratory finding), symptom, or disease temporally associated with the use of a study drug, whether or not considered related to the study drug.

AEs will be coded using the MedDRA (version 23.0) and collected from the time the participant signs the informed consent form (ICF) until Day 28.

7.2.1 Treatment-Emergent Adverse Events

A TEAEs is defined as an AE that emerged or worsened in severity after the first administration of study drug.

7.2.2 Adverse Event Severity

Grading the severity of AEs will use the Common Terminology Criteria for Adverse Events (CTCAE) grading system, version 5.0 (████████), as described below. The clinical significance of the AE is determined by the Investigator. The Investigator is encouraged to consult with the Medical Monitor.

For AEs or laboratory abnormalities not listed in the CTCAE grading system, please use the grading scale as described below.

Table 1: Adverse Event Severity Grading Terminology

CTCAE Grade	Common Terminology	Description ^a
Grade 1	Mild	asymptomatic or mild symptoms; clinical or diagnostic observations only; intervention not indicated
Grade 2	Moderate	minimal, local or noninvasive intervention indicated; limiting age appropriate instrumental ADL ^b

CTCAE Grade	Common Terminology	Description ^a
Grade 3	Severe	Severe or medically significant but not immediately life-threatening; hospitalization or prolongation of hospitalization indicated; disabling; limiting self-care ADL ^c
Grade 4	Life-threatening	Life-threatening consequences; urgent intervention indicated
Grade 5	Death	Death related to AE

^a A semi-colon indicates 'or' within the description of the grade.

^b Instrumental activities of daily living (ADL) refer to preparing meals, shopping for groceries or clothes, using the telephone, managing money, etc.

^c Self-care ADL refer to bathing, dressing and undressing, feeding self, using the toilet, taking medications, and not bedridden.

7.2.3 Adverse Event Relationship to Study Drug

The Investigator will assess the relationship between study drug and the occurrence of each AE. The Investigator's assessment of the relationship of each AE to study drug will be recorded in the source documents and on the eCRF. Alternative causes, such as medical history, concomitant therapy, or other risk factors, and the temporal relationship of the event to the study drug should be considered and investigated, if appropriate. The relationship or association of the AE to a study drug (PLN-74809 or placebo) should be assessed using clinical judgment and the following considerations:

No: Evidence exists that the adverse event has an etiology other than the study drug. For SAEs, an alternative causality must be provided (e.g., preexisting condition, underlying disease, intercurrent illness, or concomitant medication).

Yes: A temporal relationship exists between the AE onset and administration of the study drug that cannot be readily explained by the participant's clinical state or concomitant therapies. Furthermore, the AE appears with some degree of certainty to be related, based on the known therapeutic and pharmacologic actions or AE profile of the study drug. In case of cessation or reduction of the dose, the AE abates or resolves and reappears upon re-challenge.

The relationship to study procedures (such as venipuncture) should be assessed using the following considerations:

No: Evidence exists that the AE has an etiology other than the study procedure.

Yes: The AE occurred as a result of protocol-mandated procedures

The relationships will be summarized using "Yes" or "No" for "Related to Investigational Product" and "Related to Trial Procedure".

7.2.4 Serious Adverse Events

A SAE is defined as an AE that meets at least one of the following serious criteria:

- Is life-threatening
- Results in death
- Requires inpatient hospitalization (i.e., admission, overnight stay) or prolongs existing hospitalization
- Results in persistent or significant disability/incapacity
- Is a congenital anomaly/birth defect

An AE is considered life-threatening if, in the opinion of either the Investigator or the Sponsor, its occurrence places the participant at immediate risk of death. It does not include an AE that, had it occurred in a more severe form, might have caused death.

Important medical events that are not one of the preceding may be considered to be SAEs by the Investigator when, based upon appropriate medical judgement, they are considered to be clinically significant and may jeopardize the participant or when medical or surgical intervention may be required to prevent one of the outcomes listed above. (Examples of such events include allergic bronchospasm requiring intensive treatment at an emergency room or at home, blood dyscrasias, convulsions that do not result in inpatient hospitalization, or the development of drug dependency or drug abuse.)

7.2.5 Adverse Event Summaries

All AEs (serious and non-serious) occurring after study drug administration and by Day 28 of the study, regardless of relationship to study drug, will be included and classified by SOC and PT using MedDRA.

For TEAEs, the following will be summarized and presented for the Safety Set.

- i. An overall summary of TEAEs, which includes:
 - a. the number and percentage of participants experiencing a TEAE
 - b. the number and percentage of participants experiencing a TEAE by strongest relationship to investigational product
 - c. the number and percentage of participants experiencing a TEAE by strongest relationship to trial procedure
 - d. the number and percentage of participants experiencing a TEAE by greatest severity
 - e. the number and percentage of participants experiencing a TEAE with NCI CTCAE version 5.0 Grade 3 or higher
 - f. the number and percentage of participants experiencing a treatment emergent serious adverse event (TESAE)
 - g. the number and percentage of participants experiencing a TESAE by strongest relationship to investigational product
 - h. the number and percentage of participants experiencing a TESAE by strongest relationship to trial procedure

- i. the number and percentage of participants experiencing a TEAE leading to death
- j. the number and percentage of participants experiencing a TEAE which leads to a premature withdrawal
- ii. the number and percentage of participants experiencing a TEAE by SOC and PT
- iii. the number and percentage of participants experiencing a TEAE by SOC, PT and the strongest relationship to investigational product
- iv. the number and percentage of participants experiencing a TEAE by SOC, PT and the strongest relationship to trial procedure
- v. the number and percentage of participants experiencing a TESAE by SOC, PT and the strongest relationship to trial procedure

In the overall summary of TEAEs table (i), besides tabulating the number and percentage of participants, the total number of TEAE episodes will also be provided. If a participant has repeated episodes of a particular TEAE, all episodes will be counted in the summary table.

In the remaining summary tables, the incidence of TEAEs will be calculated by dividing the number of participants who have experienced the event by the total number of participants in the Safety Set. Thus, the incidence of TEAEs is shown in terms of the total number of participants and not in terms of the total number of episodes. If a participant has repeated episodes of a particular TEAE, only the most severe episode, or the episode with the strongest causal relationship, will be counted in the summary tables.

A participant with more than one type of TEAE in a particular SOC or PT will be counted only once in the total of participants experiencing TEAEs in that particular SOC or PT.

All occurrences of all AEs and SAEs will be listed for each participant, grouped by treatment arm. The listing will contain the following information: treatment arm, verbatim term, SOC, PT, severity, related to investigational product, related to trial procedure, date and day of onset, date and day of resolution, action taken with regard to study drug, treatment given to treat the adverse event, the outcome, whether the event was an SAE, SAE criteria (if applicable), whether it led to study withdrawal, and whether it is a TEAE. Listings will be sorted by treatment arm, participant identification number, onset date, SOC, and PT. If the onset date is completely missing, then these events will be presented first. If the onset date is missing a month or a day, then these events will be presented before any complete dates.

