## 11 EARLY DISCONTINUATION OF STUDY OR INDIVIDUAL PARTICIPANTS

The Investigator may withdraw a participant from the study or discontinue study drug for any of the following reasons:

- Noncompliance with protocol procedures, including those relating to administration of study drug
- Occurrence of an SAE or intolerable AE
- Occurrence of a clinically significant change in a laboratory parameter
- [REDACTED]
- [REDACTED]
- Termination of the study by the Sponsor or Investigator
- The participant requests to be discontinued from the study

Participants who discontinue study drug (regardless of reason) will be asked to remain in the study to complete all remaining assessments until hospital discharge or Day 28, whichever is sooner, unless they withdraw consent or are lost to follow-up. If this is not feasible, the participant will be assessed for an early termination visit. All assessments that are required at the last study visit, as shown in [Appendix 1](#), should be completed for any participant who is withdrawn from the study or prematurely discontinues study drug and does not agree to complete all remaining assessments.

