### 12.5 Primary Endpoint

The primary endpoint is the nature and proportion of TEAEs between PLN-74809 and placebo groups (descriptive).

Safety data from all participants who received at least one dose of study drug will be incorporated into the final safety analysis. Further details of the safety analyses will be provided in the SAP. AEs will be collected from the time the participant signs the ICF until Day 28. TEAEs are defined as AEs that emerged or worsened in severity after the first administration of study drug.

AEs will be coded using the Medical Dictionary for Regulatory Activities (MedDRA®). All AEs will be graded for severity per the CTCAE grading scale and listed by participant and summarized by last treatment taken at onset of AE. All AEs will be listed by participant and summarized by last treatment taken at onset of AE.

The incidence of AEs, the incidence of TEAEs, the incidence of treatment-related AEs, and the severity of AEs will be summarized by system organ class, preferred term, and maximum severity. In cases where a participant reports multiple occurrences of the same event (preferred term), the greatest severity will be included in the summary. The number and percentage of participants with SAEs and treatment-related SAEs and participants who withdraw prematurely due to an AE will be tabulated by study treatment and dose.

Clinical laboratory test parameters will be graded using the CTCAE grading scale for individual participants and values outside the reference ranges will be flagged. The incidence of treatment-emergent laboratory abnormalities will be summarized by severity and treatment group. For each parameter, summary statistics will be calculated for each measure and summarized by treatment and dose.

[REDACTED]

Vital sign measurements, other laboratory tests, concomitant medications, medical history and changes in physical examinations at each time point will be listed by participant.

[REDACTED]

Concomitant medications will be coded using the most current WHO drug dictionary available.

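### Does the SAP's row for TEAEs leading to premature withdrawal hide participants who stop study drug for an adverse event but stay in the study?

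*SAP*

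**What the plan says.** Item i(j) of the overall TEAE summary in SAP section 7.2.5 is "the number and percentage of participants experiencing a TEAE which leads to a premature withdrawal". Its source is Protocol section 12.5, where "participants who withdraw prematurely due to an AE will be tabulated by study treatment and dose". Neither says what is being withdrawn from.

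Elsewhere the documents keep two events apart. SAP section 3.2.4 refers to a participant who is "withdrawn from the study or prematurely discontinues study drug", and Protocol section 11 sets the default after stopping drug: "Participants who discontinue study drug (regardless of reason) will be asked to remain in the study to complete all remaining assessments", up to hospital discharge or Day 28.

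The adverse event listing in SAP section 7.2.5 has a separate field for each event: "action taken with regard to study drug" and "whether it led to study withdrawal".

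Two other summaries touch on stopping. SAP section 5.1: "Participant disposition including study completion status and reasons for early termination (if applicable) will be tabulated by treatment arm and overall". SAP section 7.1: "The number of tablets received, the occurrence of dose interruption, the duration of interruption, and total amounts of PLN-74809 in mg will be tabulated".

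**The concern.** Stopping drug because of an adverse event is a direct measure of tolerability, and here it is meant to be separable from leaving the study. If a programmer builds item i(j) from the study-withdrawal field of the listing, a participant who stops drug for an adverse event and stays in follow-up is not in the row. The better the sites retain participants, the lower the row reads.

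The neighbouring tables do not obviously make up for it. The disposition table names study completion and early termination. The exposure table gives tablets, interruptions and milligrams without a reason for stopping. Because dosing also ends at hospital discharge, a short course does not by itself indicate intolerance. A reader with only the summary tables could take a zero in item i(j) to mean that nobody stopped drug for an adverse event.

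**Working it through.** The plan states no figure on this point, so there is none to reproduce. The check is of wording, followed by an illustration of size.

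**Step 1: the possible readings of item i(j).**

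| Reading | Stops drug for a TEAE, stays in study | Consequence |
|---|---|---|
| Withdrawal from the study | Not counted in i(j) | Count comes from the listing |
| Withdrawal from study drug | Counted in i(j) | No gap |
| Either event | Counted in i(j), together with study withdrawals | No participant missed; the listing separates the two |

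Only the first reading leaves the gap.

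**Step 2: which reading the text supports.** SAP section 3.2.4 and Protocol section 11 attach withdrawal to the study and prematurity to the drug. Item i(j) borrows one word from each phrase, so those sections favour neither reading. The listing field on study withdrawal leans towards the first. The field on action taken sits in the same sentence, however, and could equally feed the row. The readable text does not settle the matter.

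Some text that could bear on it is blacked out: Protocol section 6.2 on dose modification and interruption, Protocol sections 9 and 10, several stopping reasons in Protocol section 11 and SAP section 3.2.4, the dosing text in SAP section 3.2.3, and parts of Protocol section 12.5. Absence of a definition can therefore be asserted only for the readable text.

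**Step 3: what is lost under the first reading.** The TEAE itself still enters items i(a) to i(e) and tables ii to iv, and the serious-event and fatal-event rows where it qualifies. Protocol section 8.2 has the investigator record the action taken on study drug for each adverse event, and the SAP lists that field by participant within arm. What is absent is a ready-made count by arm, not the data for it.

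**Step 4: size, as an illustration.** From the design: 12 planned per cohort, 9 active and 3 placebo (SAP section 3.1), and one cohort run (SAP section 1). Assumed: x active participants stop drug for a TEAE and all stay in the study. Intervals are exact (Clopper-Pearson) 95%; for 0/n the upper limit is 1 − 0.025^(1/n).

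- Item i(j), study reading: 0/9 = 0%, upper limit 1 − 0.025^(1/9) = 33.6%.
- Drug stops, x = 1: 1/9 = 11.1% (0.3 to 48.2%).
- Drug stops, x = 2: 2/9 = 22.2% (2.8 to 60.0%).
- Drug stops, x = 3: 3/9 = 33.3% (7.5 to 70.1%).

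If early termination left fewer active participants (also assumed), one stop is 1/6 = 16.7% (0.4 to 64.1%) or 1/3 = 33.3% (0.8 to 90.6%). The intervals are so wide that, at this size, the useful information is which participant stopped and for which event. The listing gives exactly that.

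**The case for a change.** The case for a change is respectable. Safety and tolerability is the primary objective. Stopping drug while remaining in follow-up is the intended course, not an exception, and an adverse event is a named reason for it. The remedy would be cheap: one defining phrase and one row from a field already collected. A summary table whose label can be read in more than one way is untidy whatever the sample size.

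Part of this stands. The label is ambiguous, and on the study reading the summary tables alone do not give the count.

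The rest is weaker. The argument needs the study reading, and the text does not settle on it; on the drug reading the requested count is already item i(j). Nor is the disposition table clearly confined to leaving the study. Its stated content is introduced as inclusive rather than complete, and the schedule of events puts end of treatment and early termination under one heading. Finally, no passage promises a separate row for drug discontinuation. Item i(j) carries the protocol's wording faithfully, so the two documents do not conflict.

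**Conclusion.** This is a gap that analysts will fill sensibly, and no change to the plan is needed. Item i(j) leaves open which event it counts. The programming team has to choose when the table is built, and an ordinary table footnote can state the choice. Under any choice, every TEAE is counted, every adverse event is listed by participant and arm with the action taken on study drug, and no test or decision rule uses the row.

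The most that can go wrong is a row reading 0/9 where one to three of nine active participants (11 to 33%) stopped drug and stayed. A reader could correct that from a listing of a cohort planned at 12.

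This rests on three assumptions: that the cohort actually enrolled was about the planned size or smaller, since the documents do not give the number; that sites completed the action-taken field as the protocol requires; and that the redacted text contains nothing that fixes the term in a conflicting way. In a larger trial, where a listing cannot be counted at sight, a separate drug-discontinuation row would be worth asking for. Here it adds almost nothing.
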